Appendix A. Dose Intensity Calculations

Dose intensity is calculated for each drug component and expressed as an average dose per unit of time. In this study, we choose the time unit to be week.

1. The formula for Actual Dose Intensity (mg/m²/wk or mg/wk) is defined as:

$$\text{Actual Dose Intensity (mg/m}^2\text{/wk or mg/wk)} = \frac{\text{Cumulative actual dose (mg or mg/m}^2\text{)}}{\text{Duration of exposure (wk)}}$$

- Cumulative actual dose (mg or mg/m²) received of carfilzomib and dexamethasone is defined as the cumulative dose of carfilzomib/dexamethasone, respectively, a subject received during the treatment period of the study.
- Duration of exposure (weeks) is defined as
$$\frac{(\text{last dose date} - \text{first dose date}) + \text{planned interval to next treatment week}}{7 \text{ days}}$$

Carfilzomib dosing schedule and planned interval

Cycle	Cycle Day of Treatment	Dose (mg/m ²)	Interval (Days) to Next Planned Treatment Week (or Completion)
1	Day 1	20	7
	Day 8	56 if Cohort 1; Cohort 4; Arm 3 70 if Cohort 2; Arm 1; Arm 2	7
	Day 15	56 if Cohort 1; Cohort 4; Arm 3 70 if Cohort 2; Arm 1; Arm 2	14
2 -18	Day 1	56 if Cohort 1; Arm 3 70 if Cohort 2; Cohort 4; Arm 1; Arm 2	7
	Day 8	56 if Cohort 1; Arm 3 70 if Cohort 2; Cohort 4; Arm 1; Arm 2	7
	Day 15	56 if Cohort 1; Arm 3 70 if Cohort 2; Cohort 4; Arm 1; Arm 2	14

Dexamethasone dosing schedule and planned interval

Cycle	Cycle Day of Treatment	Dose (mg)	Interval (Days) to Next Planned Treatment
1 - 8	Day 1	40	7
	Day 8	40	7
	Day 15	40	7
	Day 22	40	7
9 -18	Day 1	40	7
	Day 8	40	7
	Day 15	40	14

Lenalidomide dosing schedule and planned interval

Cycle	Cycle Day of Treatment	Dose (mg)	Interval (Days) to Next Planned Treatment
1 - 18	Day 1 - 7	25	7
	Day 8 – 14	25	7
	Day 15 - 21	25	7

2. The formula for Planned Dose Intensity (mg/m²/wk or mg/wk) is defined as:

$$\text{Planned Dose Intensity (mg/m}^2\text{/wk or mg/wk)} = \frac{\text{Cumulative planned dose (mg/m}^2\text{ or mg)}}{\text{Number of protocol specified treatment weeks}}$$

- Number of protocol specified treatment weeks is the sum of treatment weeks the patient completed. It is counted by 4 weeks for a completed or skipped cycle. For the last cycle, use the following rules to count:

Carfilzomib

1 week if the last dose is on Day 1;
2 weeks if the last dose is on Day 8;
4 weeks if the last dose is on Day 15;

Example: Patient's last carfilzomib is on cycle 2 Day 8. The number of protocol specified treatment weeks is D=4x1+2=6 weeks.

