Dexamethasone

1 week if the last dose is on Day 1;
2 weeks if the last dose is on Day 8;
3 weeks if the last dose is on Day 15 in Cycle 1 to 8;
4 weeks if the last dose is on Day 15 after Cycle 8 or Day 22;

Lenalidomide

1 week if the last dose is on Day 1-7;
2 weeks if the last dose is on Day 8-14;
4 weeks if the last dose is on Day 15- 21;

- Cumulative planned dose for each drug is the sum of protocol specified doses across the treatment weeks as determined above. Per study treatment regimen on protocol:

Carfilzomib cumulative planned dose:

For Cohort 1; Arm 3: [20, 56, 56, 0], [56, 56, 56, 0]

For Cohort 2, Arm 1; Arm 2: [20, 70, 70, 70], [70, 70, 70, 0]

For Cohort 4: [20, 56, 56, 0], [70, 70, 70, 0]

Dexamethasone cumulative planned dose:

[40, 40, 40, 40], repeated 7 more times, [40, 40, 40, 0]

Lenalidomide cumulative planned dose:

[25, 25, 25, 25, 25, 25, 25], [25, 25, 25, 25, 25, 25], [25, 25, 25, 25, 25, 25, 25],
[0, 0, 0, 0, 0, 0, 0],

3. Relative dose intensity is calculated as actual dose intensity / planned dose intensity
and expressed as a percent.

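### SAP Appendix A times lenalidomide exposure by one rule and the planned weeks by another, so relative dose intensity is not 100% for a fully compliant subject who stops at the end of a dosing week

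*SAP*

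**What the plan says.** SAP Appendix A works drug by drug: "Dose intensity is calculated for each drug component and expressed as an average dose per unit of time". Actual intensity is cumulative dose divided by duration of exposure. Duration is the days from first to last dose plus the "planned interval to next treatment week", divided by 7.

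For lenalidomide the interval comes from the table titled "Lenalidomide dosing schedule and planned interval". Its three rows (Days 1-7, 8-14 and 15-21) all give 7 days.

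Planned intensity is cumulative planned dose divided by protocol-specified treatment weeks. For earlier cycles, "It is counted by 4 weeks for a completed or skipped cycle". For the last lenalidomide cycle the count is "1 week if the last dose is on Day 1-7", "2 weeks if the last dose is on Day 8-14" and "4 weeks if the last dose is on Day 15- 21".

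The planned lenalidomide doses for the three dosing weeks are printed as "25, 25, 25, 25, 25, 25, 25], [25, 25, 25, 25, 25, 25], [25, 25, 25, 25, 25, 25, 25", which is seven, six and seven entries. The Protocol (Section 9.2.1) and the SAP's own lenalidomide table both have daily dosing on Days 1 to 21.

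SAP Section 5 defines the first and last dose dates by reference to any study drug. Appendix A does not say whether those dates or drug-specific dates enter its formula.

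**The concern.** Lenalidomide is taken daily. After a Day 7 or Day 14 dose the next planned dose is one day later, and after Day 21 it is eight days later. A constant 7 days is wrong for all three. The planned side counts whole blocks, so numerator and denominator cover different stretches of time for the same subject.

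Relative dose intensity is a listed exposure output for each drug (SAP Section 9.6.7), and extent of exposure is part of the primary safety endpoint (SAP Section 2.1). Four of the six dosing groups have 9, 9, 10 and 12 subjects (SAP Table 1), and minimum and maximum are reported (SAP Section 9.1). In a group of 9, one compliant subject who stopped on Cycle 1 Day 7 would lower the mean by (100 − 53.8)/9 = 5.1 points and could supply a minimum near 54%. That would look like underdosing that did not happen.

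**Working it through.** **Inputs.** From SAP Appendix A: the duration formula, the interval tables and the planned-week counts. From the Protocol: 25 mg daily on Days 1-21 of a 28-day cycle, so 21 × 25 = 525 mg per cycle. Assumed: lenalidomide-specific dose dates, every dose taken on schedule.

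**The SAP's own example.** For a last carfilzomib dose on Cycle 2 Day 8, the SAP counts 4×1 + 2 = 6 planned weeks. The actual rule gives ((36 − 1) + 7)/7 = 6.0. They agree.

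**Control, time rules only.**
- Carfilzomib, last dose on Day 1, 8 or 15: (0+7)/7 = 1, (7+7)/7 = 2, (14+14)/7 = 4. Planned: 1, 2, 4.
- Dexamethasone in Cycle 1, Day 1, 8, 15 or 22: 1, 2, 3, 4 by both rules. Cycle 9 Day 15: (224+14+14)/7 = 36, and planned 8×4 + 4 = 36.

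**Lenalidomide as written.** For a last dose on Cycle c, Day d, actual weeks = (28(c−1) + d − 1 + 7)/7. At an end-of-week stop with no dose missed, actual and planned mg are equal and cancel, so relative dose intensity = planned weeks / actual weeks.

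| Last dose | Actual weeks | Planned weeks | Relative dose intensity |
|---|---|---|---|
| C1D7 | 13/7 = 1.86 | 1 | 53.8% |
| C1D14 | 20/7 = 2.86 | 2 | 70.0% |
| C1D21 | 27/7 = 3.86 | 4 | 103.7% |
| C2D7 | 41/7 = 5.86 | 5 | 85.4% |
| C4D7 | 97/7 = 13.86 | 13 | 93.8% |
| C8D7 | 209/7 = 29.86 | 29 | 97.1% |
| C18D21 | 503/7 = 71.86 | 72 | 100.2% |

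In mg for the first row: 175/(13/7) = 94.23 mg/wk actual against 175 mg/wk planned.

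**Other readings of the last-dose date.**
- Anchored to the start of its weekly block (Day 1, 8 or 15): Day 7 and Day 14 stops give 100%. A complete Cycle 1 gives 4/((14+7)/7) = 4/3 = 133.3%, and 18 cycles give 72/71 = 101.4%.
- Last dose of any study drug: a complete Cycle 1 ending with Day 22 dexamethasone gives (21+7)/7 = 4 weeks and 100%. A subject who stops all drugs by Cycle 1 Day 7 still scores 53.8%.

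**Matched interval.** Replace 7 by 8−d for a last dose on Days 1-7, 15−d for Days 8-14 and 29−d for Days 15-21. Day 7: (6+1)/7 = 1. Day 14: (13+1)/7 = 2. Day 21: (20+8)/7 = 4. Each of these stops then scores 100%, in any cycle.

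**Delays still count.** Take the C8D7 case with one 42-day interruption, the limit that Protocol Section 5 sets for stem cell collection without further permission, handled as a late cycle start. Actual duration is 29 + 6 = 35 weeks and the result is 29/35 = 82.9%. If the planned week count were used in both terms, the result would be 100%.

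**Printed vector taken literally.** Twenty doses are 500 mg, so planned intensity is 500/4 = 125 mg/wk. Cycle 1 Day 21 then gives 136.11/125 = 108.9%, and an 18-cycle completer (9450/71.86 = 131.51 mg/wk) gives 105.2%.

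**The case against.** The strongest reply is that the low scores depend on the reading. The added term refers to treatment weeks and the table rows are weekly blocks, so a programmer might anchor the last dose to its block. The 53.8% and 70.0% then disappear, and what remains is an overstatement. The any-study-drug date changes the picture again. This part stands: no fixed direction of error can be claimed. It does not rescue the text, because each reading tested leaves at least one compliant pattern away from 100%.

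It is also fair that little rests on this number. Duration, cycles, dose counts, cumulative dose and average dose are separate outputs and are unaffected. No hypothesis test is planned (SAP Section 2.2), and expansion decisions use dose-limiting toxicities and committee review (Protocol Sections 5 and 5.4).

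A reader might infer that the formula penalises subjects who stop for toxicity and so links early stopping to low intensity. The documents do not support that. They give no reasons for or timing of lenalidomide stops, no planned analysis relates relative dose intensity to stopping, and the direction depends on the date used.

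A reader might also infer that the planned regimen was entered as 20 doses. The rule above the vector sums protocol-specified doses, and the table lists Days 8-14, so six entries are probably a slip of typing or text extraction.

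Finally, putting the same week count in both terms looks like the obvious repair. It would cancel time and hide cycle delays and transplant interruptions.

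**Conclusion.** The lenalidomide rule is wrong as written and should be corrected. The planned-week count, including 4 weeks for a last dose on Days 15-21, fits a 28-day cycle. The fault lies in the constant 7-day interval on the actual side and the unstated choice of dose dates.

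The range 53.8% to 103.7% covers end-of-week stops over Cycles 1-18, with both extremes in Cycle 1. It assumes lenalidomide-specific dates, 525 mg planned per cycle and no missed or delayed dose. It should not be read as a typical error: by Cycle 8 Day 7 the shortfall is 2.9 points, and after 18 full cycles the excess is 0.2 points. The consequence is confined to the descriptive lenalidomide relative dose intensity summary. It does not undermine the primary safety evaluation or the carfilzomib and dexamethasone time rules.

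**What to change.** In SAP Appendix A:

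1. State that lenalidomide intensity uses the calendar dates of the first and last lenalidomide dose, not the any-study-drug dates of Section 5. Delays and interruptions then stay in the duration.
2. Replace the fixed 7-day lenalidomide interval with the days from the last dose to the end of the counted period: 8−d for a last dose on Days 1-7, 15−d for Days 8-14 and 29−d for Days 15-21.
3. Print seven entries in week 2 of the lenalidomide planned vector, to match dosing on Days 1-21.
4. Note that mid-week stops will still score below 100%, because the whole block is charged as planned dose. With the new interval, a stop on Cycle 1 Day 1 gives 25/175 = 14.3%, as now. A stop on Cycle 1 Day 15 gives 375/525 = 71.4%, where the present rule gives (375/3)/131.25 = 95.2%.

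The cost is a few lines of appendix text and one derivation, with no new data.

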Treatment regimen(s):	
Dose-evaluation Component
 
Carfilzomib combination therapy will be given for up to 18 cycles. The combination regimens evaluated in the Dose-evaluation Component include:
 
Cohort 1 (RRMM): KRd = carfilzomib 20/56 mg/m²/ lenalidomide 25 mg/ dexamethasone 40 mg Carfilzomib dosing: 20 mg/m² Day 1 of Cycle 1; 56 mg/m² Days 8 and 15 of Cycle 1; Days 1, 8, and 15 of Cycle 2 and beyond
 
Cohort 2 (RRMM): KRd = carfilzomib 20/70 mg/m²/ lenalidomide 25 mg/ dexamethasone 40 mg Carfilzomib dosing: 20 mg/m² Day 1 of Cycle 1; 70 mg/m² Days 8 and 15 of Cycle 1; Days 1, 8, and 15 of Cycle 2 and beyond
 
Optional Cohort 3 (RRMM): KRd = carfilzomib 20/70 mg/m²/ lenalidomide 10 mg/ dexamethasone 40 mg Carfilzomib dosing: 20 mg/m² Day 1 of Cycle 1; 70 mg/m² Days 8 and 15 of Cycle 1; Days 1, 8, and 15 of Cycle 2 and beyond
 
Cohort 4 (NDMM): 2-step-up KRd = carfilzomib 20/56/56/70 mg/m²/ lenalidomide 25 mg/ dexamethasone 40 mg. Carfilzomib dosing: 20 mg/m² Day 1 of Cycle 1; 56 mg/m² on Days 8 and 15 of Cycle 1; 70 mg/m² on Days 1, 8, and 15 of Cycle 2 and beyond
 
KRd will be given in 28-day cycles:
 
• Carfilzomib will be administered once weekly intravenously (IV) on Days 1, 8, and 15• Lenalidomide will be administered once daily by mouth on Days 1–21.• Dexamethasone will be administered once daily by mouth or IV on Days 1, 8, and 15. Dexamethasone will also be given on Day 22 of Cycles 1–8.
Inclusion criteria:	
1. Age \geq 18 years
 
2. Able to provide written informed consent in accordance with federal, local, and institutional guidelines
 
3. Newly diagnosed or relapsed multiple myeloma
 
a. For subjects with relapsed multiple myeloma:
 
i. 1 to 3 prior lines of therapy for multiple myeloma (induction therapy followed by stem cell transplant and consolidation/maintenance therapy will be considered as one line of therapy), andii. Documented response of at least partial response (PR) to 1 line of prior therapy. Investigator assessment is acceptable as PR documentation. 
b. For subjects with newly diagnosed, transplant-eligible or transplant-ineligible multiple myeloma:
 
i. Symptomatic multiple myeloma (per International Myeloma Working Group [IMWG] diagnostic criteria) andii. No prior treatment for multiple myeloma

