9.2.1 STUDY TREATMENT ADMINISTRATION

Weekly carfilzomib/lenalidomide/dexamethasone (KRd) will be given in 28-day cycles (see [Table 4](#)):

- Carfilzomib will be administered once weekly IV on Days 1, 8, and 15
- Lenalidomide will be administered once daily by mouth on Days 1–21
- Dexamethasone will be administered once daily by mouth or by IV on Days 1, 8, and 15. Dexamethasone will also be given on Day 22 of Cycles 1–8.

Table 4 Carfilzomib/lenalidomide/dexamethasone Dosing Regimen

Day	28-day Cycles																											
	Week 1							Week 2							Week 3							Week 4						
	1	2	3	4	5	6	7	8	9	10	11	12	13	14	15	16	17	18	19	20	21	22	23	24	25	26	27	28
K	CFZ	X ^a						X							X													
R	Len	X	X	X	X	X	X	X	X	X	X	X	X	X	X	X	X	X	X	X	X							
d	Dex	X						X							X							X ^b						

CFZ= carfilzomib, Len = lenalidomide, Dex = dexamethasone.

^a Cycle 1 Day 1 carfilzomib dose level will be 20 mg/m².

^b Dexamethasone will be administered on Day 22 of Cycles 1-8 only.

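### SAP Appendix A's Cycle 1 planned carfilzomib vector for Cohort 2, Arm 1 and Arm 2 sums to 230 mg/m², against 160 mg/m² from its own dosing table and the protocol; used as written, it understates relative dose intensity in these groups

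*SAP*

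**What the plan says.** SAP 9.6.7 lists RDI among the exposure outputs, and Appendix A defines it as actual over planned dose intensity. On the planned dose, Appendix A states: "Cumulative planned dose for each drug is the sum of protocol specified doses across the treatment weeks as determined above". It then writes out week-by-week vectors. For the three groups that go straight from 20 to 70 mg/m², the line is "For Cohort 2, Arm 1; Arm 2: [20, 70, 70, 70], [70, 70, 70, 0". The line for the step-up group is "For Cohort 4: [20, 56, 56, 0], [70, 70, 70, 0", and the Cohort 1 and Arm 3 line also has 0 in week 4 of Cycle 1.

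The carfilzomib dosing table in the same appendix has three Cycle 1 rows: Day 1 at 20 mg/m², then Days 8 and 15, each reading "56 if Cohort 1; Cohort 4; Arm 3 70 if Cohort 2; Arm 1; Arm 2". A 14-day interval follows Day 15, and no later dosing day is listed.

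The protocol synopsis says of Cohort 2: "Carfilzomib dosing: 20 mg/m² Day 1 of Cycle 1; 70 mg/m² Days 8 and 15 of Cycle 1". Protocol Table 2 agrees. Protocol 9.2.1 gives the days for all groups: "Carfilzomib will be administered once weekly IV on Days 1, 8, and 15". Protocol Section 5 states that Cohort 2 dosing was the one taken into expansion Arms 1 and 2.

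**The concern.** The vector puts a 70 mg/m² dose in week 4 of Cycle 1, a week in which neither the appendix's table nor the protocol schedules carfilzomib. The entry would be used in the calculation. For the last cycle the appendix counts "4 weeks if the last dose is on Day 15", and a completed or skipped cycle also counts as 4 weeks. The fourth element is therefore added to the planned dose for anyone who reaches Cycle 1 Day 15.

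A larger planned dose lowers RDI. The effect falls only on Cohort 2, Arm 1 and Arm 2. In a dose-finding study that shows the 56 and 70 mg/m² groups in separate columns, equal adherence would look like poorer delivery in the groups going straight to 70 mg/m². SAP 2.1 makes the extent and duration of exposure part of the primary endpoint.

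**Working it through.** **Inputs.** Vectors, dosing table, week-count rules and formulas: SAP Appendix A. Group sizes: SAP 9.1.

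**Step 1: check each vector against the appendix's table (mg/m²).**

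| Groups | Cycle 1, vector | Cycle 1, table | Later cycles, vector | Later cycles, table |
|---|---|---|---|---|
| Cohort 1, Arm 3 | 20+56+56+0 = 132 | 132 | 168 | 168 |
| Cohort 4 | 20+56+56+0 = 132 | 132 | 210 | 210 |
| Cohort 2, Arm 1, Arm 2 | 20+70+70+70 = **230** | 20+70+70 = **160** | 210 | 210 |

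Only one entry fails. The excess is 230 − 160 = 70 mg/m² per subject.

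**Step 2: apply the SAP formulas.**

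- Actual dose intensity = cumulative actual dose ÷ exposure weeks, with exposure weeks = (last dose date − first dose date + planned interval) ÷ 7.
- Planned dose intensity = cumulative planned dose ÷ counted treatment weeks.
- RDI = actual ÷ planned.

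The appendix's example has a last dose on Cycle 2 Day 8: "The number of protocol specified treatment weeks is D=4x1+2=6 weeks". An on-schedule subject has exposure (35 + 7)/7 = 6 weeks, so the example reproduces. At each stopping point below, exposure weeks equal counted weeks for such a subject, and RDI reduces to cumulative actual ÷ cumulative planned dose.

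**Step 3: fully dosed, on-schedule subject in Cohort 2, Arm 1 or Arm 2, vector as written.** After c full cycles, RDI = [160 + 210(c − 1)] ÷ [230 + 210(c − 1)].

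| Last dose | Actual ÷ planned | RDI | Shortfall (points) |
|---|---|---|---|
| Cycle 1 Day 1 | 20/20 | 100% | 0 |
| Cycle 1 Day 8 | 90/90 | 100% | 0 |
| Cycle 1 Day 15 | 160/230 | 69.6% | 30.4 |
| Cycle 2 Day 8 | 300/370 | 81.1% | 18.9 |
| End of 2 cycles | 370/440 | 84.1% | 15.9 |
| End of 4 | 790/860 | 91.9% | 8.1 |
| End of 6 | 1210/1280 | 94.5% | 5.5 |
| End of 8 | 1630/1700 | 95.9% | 4.1 |
| End of 12 | 2470/2540 | 97.2% | 2.8 |
| End of 18 | 3730/3800 | 98.2% | 1.8 |

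With the table's 160 in the denominator, every row is 100%. Only the denominator changes, so a subject with reduced dosing has RDI multiplied by the same factor for the same counted weeks.

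**Step 4: same Cycle 2 Day 8 example in the other groups.** Cohort 1 and Arm 3: 132 + 56 + 56 = 244, so 244/244 = 100%. Cohort 4: 132 + 70 + 70 = 272, so 272/272 = 100%.

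**Step 5: reach.** Affected groups: 12 + 9 + 34 = 55. All listed groups: 10 + 12 + 34 + 9 + 9 + 33 = 107. Share: 55/107 = 51.4%. The pooled RRMM 70 mg/m² column (12 + 34 = 46) lies wholly in the affected groups. The pooled NDMM column (n = 18) mixes 9 Arm 1 subjects with 9 from Cohort 4. If all 18 were fully dosed for the same time, its mean would be low by 9/18 of the shortfall: 30.4/2 = 15.2 points at the Cycle 1 Day 15 extreme and 1.8/2 = 0.9 at 18 cycles.

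**The case against.** The strongest reply is that this is a one-entry slip which the SAP's own rule overrides. The rule calls for protocol doses, the table one page earlier has no week 4 dose, and the same groups' later-cycle vector ends in 0. A programmer working from the rule or the table would get 160. This stands to the extent that nothing in the documents shows which source was programmed, so every size given here is conditional. It does not remove the contradiction: the vector is the most explicit programming instruction on the page.

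Quality control under SAP 8.7 might also catch it. A check against the table, the rule or the protocol would; a check against the vector line would not. The SAP does not say which reference is used, so neither outcome can be assumed.

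The weight is limited too. The excess is a fixed 70 mg/m² and is diluted over a regimen planned for up to 18 cycles. SAP 2.2 plans no formal testing, and no dose decision described in the documents rests on RDI. All of this stands.

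A reader might infer that lenalidomide RDI is wrong in the same way. The documents do not support a definite claim. The planned list shows one entry fewer than 21 days, but that may be a text-conversion slip. The exposure interval has no clear anchor date: a full first cycle gives 4 ÷ [(20 + 7)/7] = 103.7% if it runs from the last dose, or 4 ÷ [(14 + 7)/7] = 133.3% if it runs from the start of the treatment week. Neither size nor direction can be fixed.

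**Conclusion.** The contradiction is real and confined to one entry: 230 against 160 mg/m² for Cycle 1 in Cohort 2, Arm 1 and Arm 2. If the vector is used as written, RDI is understated for every subject in these groups last dosed at Cycle 1 Day 15 or later. For full dosing, the shortfall is about 8 points after 4 cycles, 4 after 8 and 2 after 18.

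Three stronger readings should be resisted.

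- The 30.4-point shortfall is not typical; it needs a stop exactly at Cycle 1 Day 15. The documents give no treatment durations, so no column-level bias can be stated.
- Not all 55 subjects are necessarily affected. Those last dosed on Cycle 1 Day 1 or Day 8 are untouched, and their number is not given. The 107 is the sum of the group sizes in SAP 9.1; the size of the safety analysis set is not stated separately.
- The primary safety assessment is not compromised as a whole. Adverse events, dose-limiting toxicities and efficacy do not use the vector. Nor do treatment duration, cycles, number of doses, cumulative dose, average dose per administration, or missed, delayed and changed doses.

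This should be fixed because it is an error in the specification of a named output, and its reach is modest.

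**What to change.** Reconcile the fourth Cycle 1 entry of the planned carfilzomib vector for Cohort 2, Arm 1 and Arm 2 with Appendix A's own dosing table and the protocol schedule, and confirm which source the exposure programs use. As an acceptance check, run the appendix's Cycle 2 Day 8 example for a fully dosed, on-schedule subject in each group; RDI should be 100% in all of them. If RDI tables have already been produced from the vector, rerun them for the three groups and for the two pooled columns that contain them.

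The cost is one entry in the appendix and, where needed, a rerun of one output. No new data are required.

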3.1 Study Design

This is an open-label, multicenter, Phase 1b, dose-finding study of carfilzomib administered once weekly in combination with lenalidomide and dexamethasone (KRd) in 28-day cycles to subjects with multiple myeloma. Subjects may continue to receive study treatment for up to 18 cycles or until 1 or more of the following events occurs: disease progression; allogeneic stem cell transplant, initiation of non-protocol MM therapy (including maintenance KRd therapy beyond cycle 18), withdrawal from the study for any reason, study termination by the sponsor, death. Subjects who discontinued study therapy (for any reason other than progressive disease, **allogeneic stem cell transplant, death, or withdrawal of consent**) could enter active follow up for up to one year.

The study included dose-evaluation and dose-expansion, and was amended three times. The final study schema is shown in [Figure 1](#).

Figure 1. Study Schema

CFZ013 Study design (Amendment 3, Active)

Approximately 8 dose-limiting toxicity (DLT) evaluable subjects were **planned to be** enrolled into each opened dose-evaluation cohort. Dose-expansion arms 2 and 3 for RRMM and NDMM were planned to enroll approximately 30 subjects each. **The cohort safety review committee (CSRC) would review all available safety data and make recommendations regarding ongoing enrollment and opening of subsequent cohorts during the dose-evaluation components and would also select the KRd**

regimens to be evaluated in the dose-expansion components. After 3 amendments to the protocol, 6 dosing groups were enrolled, as seen in Table 1.

Table 1. KRd Dose Level Combinations

Study treatment	Cohort 1 RRMM N = 10	Cohort 2 RRMM N = 12	Arm 2 RRMM N = 34	Arm 1 NDMM N = 9	Cohort 4 ^b NDMM N = 9	Arm 3 NDMM N = 33
Carfilzomib mg/m ² , cycle 1 ^a	56	70	70	70	56	56
Carfilzomib mg/m ² , cycles 2+	56	70	70	70	70	56
Lenalidomide (mg)	25	25	25	25	25	25
Dexamethasone (mg) ^c	40	40	40	40	40	40

^a All subjects received carfilzomib 20 mg/m² on Day 1 Cycle 1.

^b Carfilzomib will be given at 56 mg/m² on Day 8 and 15 of Cycle 1; 70 mg/m² on Days 1, 8, and 15 of Cycle 2 and beyond.

^c IV or oral; Day 22 dexamethasone required only in Cycles 1–8; subjects receiving IV dexamethasone on Day 1, 8, 15 may receive dexamethasone orally on Day 22.

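### SAP Appendix A prints six lenalidomide doses in planned week 2, so planned dose sums to 500 mg per full cycle, not 525 mg; programmed as printed, relative dose intensity is inflated

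*SAP*

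**What the plan says.** Section 9.6.7 of the SAP reports relative dose intensity for each drug and refers to Appendix A for the calculation. Appendix A states: "Relative dose intensity is calculated as actual dose intensity / planned dose intensity". Planned dose intensity is the cumulative planned dose divided by the number of protocol-specified treatment weeks.

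The dose part of that ratio is defined by a rule: "Cumulative planned dose for each drug is the sum of protocol specified doses across the treatment weeks as determined above". Appendix A then writes the doses out day by day. For lenalidomide the three dosing weeks read "25, 25, 25, 25, 25, 25, 25], [25, 25, 25, 25, 25, 25], [25, 25, 25, 25, 25, 25, 25", and the fourth week is seven zeros.

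The weeks are counted as follows. For cycles before the last one, "It is counted by 4 weeks for a completed or skipped cycle". In the last cycle the count is "1 week if the last dose is on Day 1-7", "2 weeks if the last dose is on Day 8-14", and 4 weeks if the last dose is on Days 15 to 21.

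Protocol section 9.2.1 gives the schedule: "Lenalidomide will be administered once daily by mouth on Days 1–21". SAP Table 1 shows the same dose in all six enrolled groups: "Lenalidomide (mg) 25 25 25 25 25 25".

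**The concern.** The second bracket of the printed list has six entries where the first and third have seven. The list therefore covers 27 days and 20 doses of a 28-day cycle with 21 dosing days. The lenalidomide schedule table in Appendix A assigns 25 mg to Days 8 to 14, which is seven days, so the appendix contradicts itself as well as the protocol. SAP section 10 declares no departures from the protocol's analyses, so nothing suggests that the shorter week is intended.

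Planned dose sits in the denominator of relative dose intensity. If it is too low, the reported percentage is too high, never too low. One list serves every enrolled subject, and the amount and duration of study-drug exposure form part of the primary safety and tolerability endpoint (Protocol section 13.1.1, SAP section 2.1). The likely result is a table that makes adherence to planned lenalidomide look somewhat better than it was.

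**Working it through.** **Inputs**
- Printed planned list (SAP Appendix A): 7, 6, 7 and 7 entries; 25 mg in weeks 1 to 3 and 0 mg in week 4.
- Protocol schedule (section 9.2.1): once daily, Days 1 to 21 of a 28-day cycle.
- Dose (SAP Table 1): 25 mg in all groups, 10 + 12 + 34 + 9 + 9 + 33 = 107 subjects.
- Maximum weekly lenalidomide exposure for the 25 mg regimens (Protocol Table 2): 175 mg.
- Weeks counted in the last cycle: 1, 2 or 4, as set out above.

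**Step 1. Reproduce the stated weekly figure.** 7 × 25 = 175 mg, which matches Protocol Table 2. Neither document states a total per cycle.

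**Step 2. Sum the lists.**
- As printed: 175 + 150 + 175 + 0 = 500 mg per cycle, or 500/4 = 125 mg per week.
- From the schedule: 175 + 175 + 175 + 0 = 525 mg per cycle, or 525/4 = 131.25 mg per week.
- Over 18 cycles: 9,000 mg against 9,450 mg.

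**Step 3. Isolate the effect on relative dose intensity (RDI).** Let A be the actual cumulative dose, E the exposure duration in weeks, P the cumulative planned dose and W the planned weeks. Then

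RDI = (A / E) / (P / W).

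A, E and W do not depend on the printed list, so

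RDI (printed) / RDI (schedule) = P (schedule) / P (printed).

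**Step 4. Evaluate by the cycle and week of the last dose.** Each cell shows P (schedule) / P (printed) in mg and the resulting relative inflation.

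| Last cycle | Last dose Days 1–7 | Last dose Days 8–14 | Last dose Days 15–21 |
|---|---|---|---|
| 1 | 175/175, 0% | 350/325, 7.7% | 525/500, 5.0% |
| 2 | 700/675, 3.7% | 875/825, 6.1% | 1,050/1,000, 5.0% |
| 4 | 1,750/1,675, 4.5% | 1,925/1,825, 5.5% | 2,100/2,000, 5.0% |
| 18 | 9,100/8,675, 4.9% | 9,275/8,825, 5.1% | 9,450/9,000, 5.0% |

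These are multipliers. At 1.05, an RDI that should read 80% reads 84%, and one that should read 95% reads 99.75%.

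**Step 5. See what the whole formula returns.** For lenalidomide the Appendix A table sets a 7-day interval after each dosing week, so E = (last dose date − first dose date + 7)/7. For a subject who takes every planned dose until stopping:

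| Last dose | E (weeks) | A / E (mg/week) | RDI, printed list | RDI, 525 mg list |
|---|---|---|---|---|
| Cycle 1 Day 14 | (13 + 7)/7 = 2.857 | 350/2.857 = 122.5 | 122.5/(325/2) = 75.4% | 122.5/(350/2) = 70.0% |
| Cycle 1 Day 21 | (20 + 7)/7 = 3.857 | 525/3.857 = 136.1 | 136.1/125 = 108.9% | 136.1/131.25 = 103.7% |
| Cycle 18 Day 21 | (496 + 7)/7 = 71.857 | 9,450/71.857 = 131.5 | 131.5/125 = 105.2% | 131.5/131.25 = 100.2% |

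The ratio of the last two columns is the Step 4 multiplier in each row. The distance of the last column from 100% comes from the time rules, not from the missing entry.

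**The case against.** The strongest reply is that the printed list is only an illustration. The governing sentence defines planned dose through the protocol's doses, and the list is introduced as following the protocol regimen. A program written from that sentence or from the schedule table would use 525 mg and carry no error, and SAP section 8.7 requires output to be verified. This stands to the extent that the effect is conditional on the list being programmed as printed. It does not remove the defect, because the appendix then offers two planned doses, and the programmer is left to choose.

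A lost character in the text version of the PDF cannot be fully excluded. However, the bracket is well formed and its neighbours are intact, and the sponsor can settle the question from the source file.

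It is also fair to say that the consequences are modest. No formal hypothesis test is planned (SAP section 2.2). The evaluability rule for dose-limiting toxicity in Protocol section 5.4 rests on the share of planned doses received and does not refer to this list. Treatment duration, cycles received, number of doses, cumulative dose, average dose and dose changes do not use it either, so under-dosing would still be visible elsewhere in the exposure tables.

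Two stronger readings are tempting. A reader might infer that every subject's figure is 5% too high; the last-cycle week counts rule that out, as Step 4 shows. A reader might also infer that full compliance always scores above 100%; Step 5 gives 75.4% for a fully compliant subject who stops on Cycle 1 Day 14. The documents support neither.

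**Conclusion.** The printed lenalidomide list is wrong against the protocol schedule, Protocol Table 2, and Appendix A's own table and rule: 500 mg per full cycle where these give 525 mg. If programmed as printed, lenalidomide relative dose intensity is inflated, compared with the same calculation on the 525 mg list, by exactly 5% (relative) when the last dose falls on Days 15 to 21. In other cases the inflation lies between 0% and 7.7% and approaches 5% as cycles accumulate.

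This rests on two assumptions: that the six-entry bracket is in the source document, and that the program follows it. What is at risk is one descriptive exposure summary. It should be corrected because Appendix A is the operative specification for that summary.

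Appendix A's time rules are a separate matter. The 7-day interval after Days 15 to 21 does not match the 4 weeks counted on the planned side, and for a stop in week 2 the exposure time (2.857 weeks in Cycle 1) exceeds the 2 weeks planned. These mismatches also move lenalidomide relative dose intensity, and correcting the list does not cure them.

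**What to change.** Reconcile the planned lenalidomide list with the protocol schedule and the Appendix A schedule table, so that week 2 has seven entries (175 mg) and the cycle sums to 525 mg. Confirm which source the derivation program uses, and correct the program if it carries the printed list.

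Add a program check that the sum of each planned list, by week and by cycle, matches the schedule table. Counting entries is not enough. In the same part of Appendix A the Cycle 1 carfilzomib list for Cohort 2, Arm 1 and Arm 2 has the expected four entries but sums to 20 + 70 + 70 + 70 = 230 mg/m². The schedule table has no fourth-week dose and sums to 20 + 70 + 70 = 160 mg/m². An entry count would pass that list, and those two places also need to be reconciled.

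Take up the lenalidomide exposure-time and planned-week rules at the same time, as a separate item.

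The cost is one entry in the SAP, a short check and, if needed, one line of code. No new data are required.
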